## **2.1 Background**

Kidney transplant is the ultimate treatment for end stage renal disease. It improves the quality of life and survival of the patient. Acute kidney injury (AKI) caused by ischemia reperfusion occurs to some extent in cadaveric renal allografts , invariably in the non-beating heart setting and in some live donor transplants leading to varying degrees of delayed graft function (DGF). DGF due to AKI is defined as the need for dialysis in the first week after transplantation and complicates 4-10% of live donor and 5-50% of cadaveric kidney transplants.i Several lines of experimental evidence suggest that ischemia reperfusion injury (I/R) plays a critical role in the pathogenesis of DGF. The kidney with its high adenosine triphosphate (ATP) consumption and complex vascular architecture is particularly vulnerable to I/R injury. A variety of therapeutic measures have been implemented to decrease the incidence of DGF.ii These measures include maintenance of normovolemia, avoidance of arterial hypotension, and avoidance of nephrotoxic drugs in the recipient. Minimizing cold and warm ischemia time have also been advocated to minimize graft injury; however, these measures have not significantly decreased the rate of occurrence of DGF after kidney transplantation.iii, iv Given the increasing demand for kidney allografts, new diagnostic and therapeutic measures are needed to reduce AKI and DGF following kidney transplant and to improve outcome.v, vi,

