### **2.3.1 Neutrophil gelatinase associated lipocalin (NGAL)**

Neutrophil gelatinase associated lipocalin (NGAL) is normally secreted by renal tubular cells, lymphocytes, and cardiomyocytes in response to cytosolic or pericellular catalytic iron liberated during ischemic or toxic injury. NGAL released in blood is freely filtered by the glomerulus; however, most NGAL is reabsorbed in the proximal tubule by megalin-dependent endocytosis. This is supported by experimental evidence that systemic injection of labeled NGAL becomes enriched in the proximal tubule but does not appear in the urine of animals.xlvi The presence of urine NGAL is a reflection of proximal tubular injury that precludes NGAL reabsorption and/or increased *denovo* NGAL synthesis. Gene expression studies in AKI have demonstrated massive up-regulation of NGAL mRNA in the distal nephron segments specifically in the thick ascending limb loop of Henle and collecting ducts. This increased synthesis of NGAL in the distal nephron segments accounts for most of the NGAL observed in the urine.xlvi, xlvi Mishara et al examined protocol biopsy specimens in thirteen cadaveric and twelve living- related allografts within one hour of reperfusion for NGAL expression by immunochemistry. Staining intensity for NGAL correlated well with cold ischemia time, peak post-transplant serum creatinine, and requirement of dialysis.xlvi In another study of 33 cases, urine NGAL on the day of transplant surgery was a predictor of DGF with an AUC of 0.9 (Needs reference). Importantly, serum creatinine level peaked after two to four days. Kusaka et al found urine NGAL as a good predictor of recovery from DGF (Needs Reference). In addition, clinical studies suggest that measurement of urine NGAL has several advantages: urine NGAL permits prediction of DGF with adequate urine output and decreasing creatinine, low urine NGAL levels in oliguric patients after kidney transplantation suggests reversible hypovolemia and hypoperfusion, urine NGAL predicts prolonged DGF, and urine NGAL provides a simple non-invasive test to quantify recovery from kidney injury. If urine NGAL reaches a normal value, subsequent rises suggest new kidney injury.xlvi Indeed, emerging evidence suggests urine NGAL is also a marker of chronic kidney disease severity. Urine NGAL levels are elevated in CKD and significantly correlate with serum creatinine, GFR and proteinuria. Levels of urine NGAL in these situations are significantly blunted compared with values measured in AKI.xlvi, xlvi, 1

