#### **4.2 Measurements**

For each patient, approximately ten milliliters of urine will be collected at zero, six, and twelve hours after transplantation, as well as, postoperative day one and two. Time zero will be defined as the time surgery is completed per documentation in the anesthesia flow sheet. Each sample will be placed in a centrifuge at 3300 RPM for three minutes. The urinary supernatant will be frozen at -80 Celsius and assayed in batches for NGAL and IL-18. Both urine NGAL and IL-18 will be quantified using ELISA testing. Serum and urine creatinine concentrations will be measured by the Jaffe assay using the P-module of a Cobas analyzer (Roche diagnostics, Indianapolis, IN) and the Beckman creatinine analyzer system (Beckman Instruments Inc., Fullerton CA).

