#### **4.3 Outcomes**

The degree of allograft injury will be assessed by the levels of urinary biomarkers NGAL, IL-18, and KIM-

1. The primary endpoints will be the level of graft function in the early post transplantation period categorized as follows: delayed graft function (DGF) (defined as the need for dialysis within the first week of transplantation), slow graft function (SGF) (defined as <40% decrease in serum creatinine by POD 3), and immediate graft function (IGF) (defined as >40% reduction in serum creatinine by POD3). Incidence of allograft primary malfunction will be based on urine output during the first three days after

transplantation, the one month serum creatinine concentration, one month estimated GFR calculated according to diet modification. Additional secondary endpoints include 90 day mortality, length of ICU stay, and length of hospital stay.

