#### **4.4 Statistical Analysis**

The sample size calculation is based on a projected difference of NGAL levels between the two study arms. Hall et al reported a mean NGAL level of 49 mg/mL (SD = 37 mg/mL) for a group of patients that had immediate graft function and a mean NGAL level of 248 mg/mL in a group of patients with slow graft function. (which Hall reference is this) Based on these data we consider a conservative estimate of a mean difference between study groups to be 35 mg/mL NGAL. Using these assumptions, an alpha level of 0.05 and 80% power, we calculate a sample size of n= 19 per study group. Variables such as biomarkers, blood pressure, creatinine, and urine output that are expressed at multiple time points will be compared between the groups using repeated measures of ANOVA. Categorical variables will be expressed as percentages and will be compared using chi-squared analysis. A  $p$  value  $<0.05$  will be considered to be a statistically significant difference.

Ref#1 Perico(2004) delayed graft function in kidney transplantation Lancet 364(9447): 1814-1827 Perico, N., et al. (2004). "Delayed graft function in kidney transplantation." Lancet **364**(9447): 1814-1827

Ref #2 (old ref #11)

Ref#3 Rabb,H(2012) The promise of immune cell therapy for acute kidney injury.journal of clinical investigation122(11):3852-54(old ref #38)

Ref#4 Perico P (2004) Delayed graft function in kidney transplantation Lancet 364(9447):1814-1827

Ref#5 Siedlecki a etal(2011) Delayed graft function in kidney transplant Am j Transplant 11 (11) :2279-2296(old ref#42)

Ref#6 (OLD REF#6)

i Perico, N., et al. (2004). "Delayed graft function in kidney transplantation." *Lancet* **364**(9447): 1814-1827

ii Eltzschig ,H k and T.Eckle (2011). Ischemia and reperfusion –from mechanisms to translation *Nature Medicine* **17**(11) :1391-1401

iii Rabb,H(2012). The promise of immune cell therapy for acute kidney injury.*journal of clinical investigation***122**(11):3852-54

iv same as #1. Perico, N., et al. (2004). "Delayed graft function in kidney transplantation." *Lancet* **364**(9447): 1814-1827

v Siedlecki a etal. (2011). Delayed Graft Function in Kidney Transplant. *Am j Transplant* **11** (11) :2279-2296

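### Repeated-measures ANOVA on five urine samples, with no missing-sample rule and no allowance on 19 per arm: a mixed model on all samples is the better choice, but the power at risk depends on assumptions

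*Combined protocol and SAP*

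**What the plan says.** Section 4.2 (Measurements) states that "approximately ten milliliters of urine will be collected at zero, six, and twelve hours after transplantation", with further samples on postoperative days 1 and 2. That makes five urine samples per patient.

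Section 4.4 (Statistical Analysis) states that biomarkers, blood pressure, creatinine and urine output, where "expressed at multiple time points will be compared between the groups using repeated measures of ANOVA", form one class of variables with one method. It gives no rule for a patient with a missing sample, no analysis set, no imputation method and no named contrast.

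The same section sets the trial's size: "The sample size calculation is based on a projected difference of NGAL levels between the two study arms". It cites a "mean NGAL level of 49 mg/mL (SD = 37 mg/mL") in patients with immediate graft function, takes a difference of 35 between arms, and with "an alpha level of 0.05 and 80% power" arrives at 19 per group. No allowance for loss is mentioned.

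Section 4.3 (Outcomes) makes the graft-function category the primary endpoint. One of its categories is "slow graft function (SGF) (defined as <40% decrease in serum creatinine by POD 3"), so a pre-transplant creatinine is already needed. Section 4.4 does not say how that value enters the repeated creatinine analysis.

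**The concern.** Conventional repeated-measures ANOVA works on complete rows, so one missing tube out of five can remove a patient together with the four samples that were collected. The 19 per arm leaves almost no slack. The only power statement in the plan is for NGAL, so any patients dropped would reduce the power on which the trial was sized.

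There is also a question of which patients would be lost. Section 2.1 says that delayed graft function "complicates 4-10% of live donor and 5-50% of cadaveric kidney transplants", and section 2.3.1 discusses oliguria after transplantation. If poor graft function were a reason for a missing sample, dropping incomplete patients would remove those whose injury the biomarkers are meant to measure, possibly unequally between arms.

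For creatinine, ignoring a pre-transplant value that the trial collects anyway gives up precision.

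**Working it through.** **Inputs.** From section 4.4: difference 35, SD 37 (units as printed), alpha 0.05, power 80%, 19 per arm. From section 4.1: 1:1 allocation. From section 4.2: five sampling times. From section 2.1: delayed graft function in 4 to 10% of live donor transplants. Assumed, because the plan does not give them: a two-sided test, the missing rate and its pattern, dropping of incomplete patients, the within-patient correlation ρ, SD 37 at every time, and the same difference at every time.

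**1. The plan's own figure.** The standardised difference is 35/37 = 0.946. By the two-sample t-test, power is 78.7% at 18 per arm and 81.0% at 19. Exactly 80% needs 18.55 per arm. The plan's 19 is reproduced, and it contains rounding only.

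**2. Loss confined to a few patients.** Suppose the 4 to 10% with delayed graft function each lacked at least one sample and were dropped.
- 19 × 0.96 = 18.24 per arm gives 79.3%.
- 19 × 0.90 = 17.10 per arm gives 76.5%.

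The fall is 1.7 to 4.5 points. If 5% of samples were missing but all in the same 5% of patients, 19 × 0.95 = 18.05 per arm gives 78.8%, a fall of about 2 points.

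**3. Loss scattered independently.** If a fraction m of samples is missing independently at each time, 19 × (1 − m)^5 patients per arm are complete. Power on the single comparison used for sizing would be:

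| m | Complete per arm | Power |
|---|---|---|
| 0% | 19 | 81.0% |
| 1% | 18.1 | 78.9% |
| 2% | 17.2 | 76.7% |
| 5% | 14.7 | 69.6% |
| 10% | 11.2 | 56.9% |

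**4. The five-time average.** The average of five samples has SD 37 × √((1 + 4ρ)/5), which is 24.5, 28.7, 32.3 and 35.5 at ρ = 0.3, 0.5, 0.7 and 0.9. With 5% missing independently, the complete-case column uses 14.7 per arm. The last column weights each patient with k samples by 1/(ρ + (1 − ρ)/k).

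| ρ | Nothing missing | Complete cases only | Fall (points) | Mixed model, all samples |
|---|---|---|---|---|
| 0.3 | 99.0% | 96.1% | 2.8 | 98.9% |
| 0.5 | 95.6% | 89.1% | 6.4 | 95.4% |
| 0.7 | 90.2% | 81.0% | 9.2 | 90.1% |
| 0.9 | 84.1% | 73.2% | 10.9 | 84.0% |

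Averaging over the random number of complete patients makes the falls slightly larger: 7.0, 9.9 and 11.5 points at ρ = 0.5, 0.7 and 0.9. With samples missing at random, the mixed model loses at most 0.2 points.

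**5. Choice of contrast.** If the 35-unit difference held only at 0, 6 and 12 hours (assumed), the five-time average difference would be 35 × 3/5 = 21. Power with nothing missing would then be 59%, 50% and 43% at ρ = 0.5, 0.7 and 0.9.

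**6. Creatinine.** Adjustment multiplies the residual SD by √(1 − r²), where r is the correlation with the pre-transplant value. An effect with 80% unadjusted power would have 84%, 90% or 98% at r = 0.3, 0.5 or 0.7 (assumed).

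**The case against.** The strongest reply is that every large figure above comes from an assumed scenario. The documents give no missing rate, do not say that incomplete patients are dropped, and do not give the correlation. A reader might infer that the trial will lose about ten points of power. The documents do not support that: such a loss needs 5% missing, independent scatter, deletion of incomplete patients and high correlation, all together. If poor graft function is the mechanism, missing samples would more naturally cluster in a few patients, which costs 2 to 4 points. This objection stands, and the size has to be stated conditionally.

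The evidence for missing urine is also thin. The statement that "low urine NGAL levels in oliguric patients after kidney transplantation suggests reversible hypovolemia and hypoperfusion" describes NGAL being measured in oliguric patients, and delayed graft function is defined by dialysis rather than by absent urine. Section 4.2 needs only about 10 mL at each time, and section 4.1 mentions bladder catheters. Missing samples are possible, but the documents do not establish them.

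A reader might also infer that a mixed model removes the problem. It recovers power for samples missing at random. It cannot recover a patient with no sample, nor does it correct for samples missing because the graft is failing.

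Finally, a mean of 49 with SD 37 suggests right skew, so a log scale is tempting. Its gain depends on the scenario. In simulation with 5% missing it added 7 to 9 points when lognormal means of 84 and 49 were compared. It added nothing material when the means were 49 and 14, or when treatment only shifted patients between function classes.

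What survives is narrower: the rule is unstated, the sample size has no slack, and a method that uses every collected sample needs no new data.

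**Conclusion.** The point holds as a gap in the plan with a cheap improvement, not as a demonstrated loss of power. The facts are firm: five urine times, repeated-measures ANOVA, no missing-sample rule, and 19 per arm that is 18.55 rounded up. Losing one patient per arm from the comparison takes the sizing test to 78.7%, below the stated 80%.

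The size is about 2 to 4 points if 4 to 10% of patients lack a sample. It is about 6 to 11 points for the five-time average if 5% of samples are missing independently, incomplete patients are dropped and the correlation is 0.5 to 0.9. At correlation 0.3 it is 3 points. At correlation 0.5 to 0.7 the five-time average still has about 81% power or more, so even that scenario need not take the trial below its planned level.

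A reader might infer that the primary endpoint is at risk. It is not: the classification into delayed, slow or immediate graft function does not use this analysis. The point should be addressed before the analysis, but it does not undermine the design.

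**What to change.** In section 4.4:

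- Replace repeated-measures ANOVA for NGAL and IL-18 (and KIM-1, if assayed) with a linear mixed model with group, time and group-by-time terms. Use all available samples and small-sample degrees of freedom.
- Name in advance the one contrast to be tested. If it is the five-time average, state that it loses power when the effect is confined to the early samples.
- Analyse creatinine with its pre-transplant value as a covariate.
- Report missing samples and their reasons by arm, and add a sensitivity analysis, for example worst-rank, for samples missing because of poor graft function.

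The log scale is optional. If it is chosen, the estimand becomes a ratio of geometric means and the power of 19 per arm must be restated. If the SD of log NGAL is √(ln(1 + (37/49)²)) = 0.672, a single comparison has 80% power for a ratio of about 0.53.

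The cost is SAP wording and modest programming. No new data or patients are needed.
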